- To assure that approval for the study is obtained from an Institutional Review Board/ Independent Ethics Committee according to legal requirements, and to comply with their requirements for on-going review and reporting.
- To comply with procedures for data recording and reporting.
- To permit monitoring, auditing and inspection by the sponsor and relevant regulatory agencies.
- To retain study related documents according to regulatory requirements and as agreed with the sponsor.

Investigator	
Name:	[name]
Function:	
Signature:	
Date:	

PROTOCOL SYNOPSIS

Study Title	A proof of concept study to investigate the use and relevance of a digital platform for infant crying and fussing
Country of Implementation	Singapore
Study Objectives	
Primary: To evaluate the real-life usability and relevance of the cry and fuss clock generated from the LENA recorder data and the level of engagement due to the content on the COOL mobile app by the primary caregiver.
 
Secondary: To evaluate the real-life usability and relevance of a digital platform for infant crying and fussing in the daily practice of the HCPs.
 
Exploratory:
 
 -To explore crying and fussing duration quantified by LENA recorder -To explore crying and fussing duration perceived by the primary caregiver. -To explore relationship between infant crying and fussing with parameters like heart rate, sleep pattern collected by Fitbit for the primary caregiver. - To explore relationship between crying captured by Cocoon Cam with LENA quantified crying and fussing. - To explore relationship between crying captured by Cocoon Cam with primary caregiver reported crying. - To explore relationship between sleep time captured by Cocoon Cam with primary caregiver reported sleep time. - To explore the real-life usability and relevance of activity log for infant cry and sleep including push notifications in the Cocoon Cam app for the primary care giver - To measure the data on usage of the Cocoon Cam app by the primary caregiver - To explore the usability of Cocoon Cam and data captured by the Cocoon Cam app for the HCP in their daily practice
Study Design	This is a single centre proof of concept
Study Population	20 infants aged 2 to 12 months of age completing the study. Consideration would be made to recruit 10 infants with > 1 hr crying every day and primary caregiver having concern about infant's crying pattern.
Study Duration	The duration of the study will be approximately 2 weeks for each subject from their primary caregiver(s)/legally acceptable representative(s) signing the informed consent until completion of end of study questionnaire For Subjects who consent for Cocoon Cam the duration of the study will be approximately 3 weeks, considering additional 1 week for set-up and training period with Cocoon Cam.
Inclusion and Exclusion Criteria	
Inclusion Criteria:
 
 1. Infants aged 2 to 12 months. 2. Primary caregiver should have reliable access to the internet and a reliable device such as a computer, tablet or smartphone to

	
access the COOL mobile app and to be able to view the LENA data and complete questionnaires.
 
 3. Primary caregiver should be adequately comfortable in English to read the content in the COOL mobile app and complete questionnaires. 4. Primary caregiver takes care of the child more than 50% of the time 
Exclusion Criteria:
 
 1. Primary caregiver who is not adequately comfortable in English language to read the content in the COOL mobile app and complete questionnaires. 2. Incapability of the primary caregiver to access COOL mobile app using a reliable device with internet.
End points	
Primary: The rating by the primary caregivers on the use and relevance of the cry and fuss clock generated from the LENA recorder data and the rating by the primary caregiver on their level of engagement due to the content on the COOL mobile app
 
Secondary: The rating by the HCPs on the use and relevance of data provided by the LENA recorder in their general practice
 
Exploratory:
 
 • Total crying and fussing time captured by the LENA recorder • Crying and fussing time perceived by the primary caregiver • Vital parameters like heart rate, sleep recorded by the Fitbit used by the primary caregiver during crying and fussing events registered by LENA • Comments and feedback provided by the primary caregiver on the LENA recorder and the COOL mobile app • Comments and feedback provided by the HCP on the LENA recorder and the data provided • Sleep time recorded by the Cocoon Cam • Crying recorded by the Cocoon Cam • Crying start and end time recorded by the primary caregiver in the COOL app • Sleep start and end time recorded by the primary caregiver in the COOL app • Comments and feedback provided by the primary caregiver and HCP on the Cocoon Cam and the activity log for infant cry and sleep including push notifications in the Cocoon Cam app • Usage data from the Cocoon Cam app
Study Description	
At screening visit, after parent(s)/guardian(s) of potential subjects and/or legal representatives have been informed about the study, they will be requested to sign the informed consent form (ICF) prior to start of the study. After successful signing of the informed consent, the investigator will assess the eligibility of the subjects. If the subject meets all the inclusion and none of the exclusion criteria, the primary caregiver will complete a detailed questionnaire on subject's demographics, birth, family, feeding characteristics and primary caregiver's characteristics. The primary caregiver will be provided the LENA recorder kit and in case consented for Fitbit, they will be provided with the Fitbit. The primary caregiver will need to complete a training period in order to verify subject's primary caregiver's ability to properly connect, operate and upload data using the LENA

	
recorders and uploader. As part of the training period, the primary caregiver will do 1-2 hours of recording using the LENA recorder and successfully upload the data into the LENA cloud server through the internet. Once the study coordinator verifies that the upload is successful, the training and feasibility assessment will be considered as complete and the subject will be considered as enrolled. The primary caregiver of the enrolled subject will be provided access to the COOL mobile app and the recording period will start.
 
During the recording period, the subject will be using the LENA recorder and will complete a daily questionnaire at the end of each day. At the end of 7 days, the site will perform a phone call and the LENA cry and fuss clock generated from the LENA recorder data for the recorded period will be shared with the primary caregiver through the COOL mobile app. After viewing the cry and fuss clock, the primary caregiver will need to complete a questionnaire on the use of LENA recorder and the content of the COOL mobile app. The primary caregiver will continue using the LENA recorder for the next 7 days. At the end of 14 days, the LENA cry and fuss data for the recorded period will be shared with the primary caregiver and the primary caregiver will need to complete another questionnaire on the use and relevance of the cry and fuss clock and overall relevance of the COOL mobile app. At the end of the recording period, the primary caregiver will schedule an appointment with the PI. If the primary caregiver consents for the use of Fitbit, they will be provided Fitbit to record their vital parameters like heartrate and sleep pattern through the 14 days after enrolment. At the end of study visit, the primary caregiver will discuss the data provided by the LENA recorder and the COOL mobile app with the PI and PI will use the data to explain to the primary care giver if there is any specific cry pattern that could be assessed based on the objective data from LENA. The Primary caregiver and PI will complete a questionnaire each on the use of the data provided by the LENA recorder during their discussion.
 
For up to 5 subjects in the study, if the primary caregiver consents for the use of Cocoon Cam they will be provided with the Cocoon Cam kit at screening visit. The primary caregiver will need to complete a training period to verify the ability to properly connect, operate and upload data using the LENA recorders and uploader as well as the Cocoon Cam. As part of the training period, the primary caregiver will have to
 
 I) perform 1-2 hours of recording using the LENA recorder II) successfully upload the data into the LENA cloud server through the internet, III) use the Cocoon Cam for 1 day, and IV) be able to start using the Cocoon Cam application. 
Once the study coordinator verifies that the LENA upload is successful and Cocoon Cam set-up is complete, the training and feasibility assessment will be considered as complete and the subject will be considered as enrolled. The primary caregiver of the enrolled subject will be provided access to the COOL mobile app and the recording period will start. During the recording period, in addition to the daily questionnaire, the primary caregiver need to enter cry and sleep time using the COOL app. At the end of 7th day and 14th day, the primary caregiver need to complete questionnaires on the usability of the Cocoon Cam.

Statistical Consideration	
Because of the exploratory nature of this study, no formal sample size calculation will be performed. This study plans to have 20 completed subjects. Considering a 20% drop-out rate, approximately 25 subjects are planned to be enrolled.

Assuming a standard deviation of 1.25 for the primary rating score, 20 subjects will achieve a half-width of at most 0.70 for the two-sided 95% confidence interval with a conditional probability of 0.90.

The overall probability of achieving this precision in capturing the true mean is the product of the half-width probability and the confidence level, which is 0.855.

TABLE OF CONTENTS

PROTOCOL SIGNATURE PAGE - SPONSOR	2
PROTOCOL SIGNATURE PAGE - INVESTIGATOR	3
PROTOCOL SYNOPSIS	4
TABLE OF CONTENTS	8
ABBREVIATIONS AND DEFINITIONS	11
1 INTRODUCTION	12
2 STUDY OBJECTIVES	12
2.1 Primary study objective	12
2.2 Secondary study objective	13
2.3 Exploratory study objective(s)	13
3 STUDY DESIGN	13
3.1 Study design	13
3.2 Study description	13
3.3 Schematic diagram of study design (*Use of Fitbit and Cocoon Cam is based on Consent given)	14
3.4 Study Centres	15
3.5 Duration of the study per subject	15
4 SUBJECTS	15
4.1 Study population	15
4.2 Inclusion criteria	15
4.3 Exclusion criteria	15
4.4 Subject recruitment	15
4.5 Instructions and restrictions during the study	15
4.6 Subject discontinuation during the study	16
4.6.1 Criteria for subject discontinuation	16
4.6.2 Procedures in case of subject discontinuation	16
5 STUDY PARAMETERS	16
5.1 Primary outcome parameter	16
5.2 Secondary outcome parameter	16
5.3 Exploratory outcome parameter(s)	17
5.4 Safety parameters	17
5.5 Other parameters	17
5.5.1 Demographics, subject and family characteristics	17
5.5.2 Crying pattern history and primary caregiver experience	17
5.5.3 HCP Feedback	18
5.5.4 Data from Fitbit	18
5.5.5 Data from Cocoon Cam	18
5.5.6 Protocol compliance	18
6 STUDY PROCEDURES AND ASSESSMENTS	18
6.1 Procedures per visit	18
6.2 Assessment windows	19
6.3 Assessments	19
6.3.1 Demographics	19
6.3.2 Birth characteristics	19
6.3.3 Household Characteristics	20

6.3.4	Relevant medical history (including pre-existing conditions)	20
6.3.5	Relevant concomitant medications	20
6.3.6	Feeding characteristics	20
6.3.7	Primary Caregivers Characteristics	20
6.3.8	Questionnaires	20
6.3.9	Data from Fitbit	21
6.3.10	Data from Cocoon Cam	21
6.3.11	Study compliance	21
6.3.12	End of study evaluation	21
7	PRODUCTS	21
7.1	Name and description of the product	21

PI	Principal Investigator
PP	Per protocol
SAE	Serious Adverse Events
SUSAR	Suspected unexpected serious adverse reactions
US	United States of America

1 INTRODUCTION

Excessive crying and fussing of unknown cause in infants is common and of relevant parental concern. All infants cry but infants who cry a lot have a variety of impacts on parents and health services. On an average, crying peaks at 4-6 weeks of age and then diminishes by 12 weeks of age [1]. In the early months, infants tend to cry most in the late afternoon and evening [2]. Although it is true that babies who cry a lot cry relatively intensely, the majority of their crying is intermittent fussing or fretting, rather than highly intense crying.

Regurgitation, infantile colic and functional constipation are common functional gastrointestinal disorders (FGIDs) during infancy. By providing complete and updated parental education, reassurance and nutritional advice, healthcare professionals can optimise the management of FGIDs and related symptoms and reduce the inappropriate use of medication or dietary interventions [3].

LENA stands for Language **EN**vironment **A**nalysis and is known as the “talk pedometer” but it provides more than just the counting of child vocalizations, conversational turns, and adult words. LENA system comprises a small digital recorder that fits in specialized clothing worn by a child. LENA provides a non-invasive and an objective method of capturing the natural sound/language environment that a child produces and/or experiences. The LENA system started its development over 10 years ago and is currently the gold standard for automated measurement of home language environments. It is used in more than 300 research institutions around the world and its use has been studied in various language environments [4-5]. It has provided research opportunities and information about vocal characteristics as markers for Autism Spectrum Disorder, early-language environment in the NICU, and assessment of language delays [6-10].

In certain research strategies, the LENA recording can be obtained throughout the day, and the audio data subsequently uploaded by the parent via a secured internet server to a cloud platform for processing (Appendix I). The cloud-based software automatically processes the data and generates metadata. The metadata or reports can be viewed electronically by the authorized users. The metadata can provide useful and quantifiable metrics to the researchers and parents. The LENA cloud-based software uses machine-learning algorithms to automatically process the recording (the audio data). The audio processing defines 8 labels that it applies to the data: to first order, every second of the audio data is labelled with one of these 8 categories – Male Adult, Female Adult, Key Child, Other Child, Overlap, Noise, TV/Electronic, Silence. Only one label applies at any point in time. The key child is the child wearing the LENA recorder. Within the utterances attributed to the key child, the algorithm further subcategorizes the key child data into vocalization, vegetative and cry period. The cry period can be further stratified into cry and fussiness. The LENA algorithm is validated in a human-rated sample of 124 cry periods from 41 infants and shows 90% sensitivity, 92% specificity, and 91% overall accuracy.

For this study, LENA recorder model# 0121 will be used to record crying and fussing of infants. This study will apply the LENA recorder to detect and quantify episodes of crying and fussing in a small cohort of infants, 2 to 12 months of age. The data collected and interpreted by the LENA system will be summarised in a daily clock and shared with the primary caregiver through a mobile application (mobile app). In addition, the primary caregiver will be provided with insights on infant's crying and fussing patterns in the mobile app. The daily crying and fussing data as interpreted by the LENA will also be shared with the HCP through a web interface. The goal of this study is to investigate the use and relevance of the data generated by the LENA system and insights shared through the mobile application in daily life of the primary caregiver. The study will also evaluate the usability of the objective cry and fuss data provided by the LENA in daily practice of the HCPs. The study will also explore any relation between vital parameters like heart rate, sleep recorded by the Fitbit used by the primary caregiver during crying events registered by LENA. The study will also explore the usability of the Cocoon Cam and its ability to record sleep and cry time for infants.

2 STUDY OBJECTIVES

2.1 Primary study objective

To evaluate the real-life usability and relevance of the cry and fuss clock generated from the LENA recorder data and the level of engagement due to the content on the COOL mobile app by the primary caregiver.

2.2 Secondary study objective

To evaluate the real-life usability and relevance of a digital platform for infant crying and fussing in the daily practice of the HCPs.

2.3 Exploratory study objective(s)

- To explore crying and fussing duration quantified by LENA recorder
- To explore crying and fussing duration perceived by the primary caregiver
- To explore relationship between infant crying and fussing with parameters like heart rate, sleep pattern collected by Fitbit for the primary caregiver.
- To explore relationship between crying captured by Cocoon Cam with LENA quantified crying and fussing.
- To explore relationship between crying captured by Cocoon Cam with primary caregiver reported crying.
- To explore relationship between sleep time captured by Cocoon Cam with primary caregiver reported sleep time.
- To explore the real-life usability and relevance of activity log for infant cry and sleep including push notifications in the Cocoon Cam APP for the primary care giver
- To measure the data on usage of the Cocoon Cam APP by the primary caregiver
- To explore the usability of Cocoon Cam and data captured by the Cocoon Cam APP for the HCP in their daily practice

3 STUDY DESIGN

3.1 Study design

This is a single centre proof of concept study

3.2 Study description

At screening visit, after parent(s)/ guardian(s) of potential subjects and/or legal representatives have been informed about the study, they will be requested to sign the informed consent form (ICF) prior to start of the study. After successful signing of the informed consent, the investigator will assess the eligibility of the subjects. If the subject meets all the inclusion and none of the exclusion criteria, the primary caregiver will complete a detailed questionnaire on subject's demographics, birth, family, feeding characteristics and primary caregiver's characteristics. The primary caregiver will be provided the LENA recorder kit and in case consented for Fitbit, they will be provided with the Fitbit. The primary caregiver will need to complete a training period in order to verify a subject's primary caregiver's ability to properly connect, operate and upload data using the LENA recorders and uploader. As part of the training period, the primary caregiver will do 1-2 hours of recording using the LENA recorder and successfully upload the data into the LENA cloud server through the internet. Once the study coordinator verifies that the upload is successful, the training and feasibility assessment will be considered as complete and the subject will be considered as enrolled. The primary caregiver of the enrolled subject will be provided access to the COOL mobile app and the recording period will start.

During the recording period, the subject will be using the LENA recorder and will complete a daily questionnaire at the end of each day. At the end of 7 days, the site will perform a phone call and the LENA cry and fuss clock generated from the LENA recorder data for the recorded period will be shared with the primary caregiver through the COOL mobile app. After viewing the cry and fuss clock, the primary caregiver will need to complete a questionnaire on the use of LENA recorder and the content of the COOL mobile app. The primary caregiver will continue using the LENA recorder for the next 7 days. At the end of 14 days, the LENA cry and fuss data for the recorded period will be shared with the primary caregiver and the primary caregiver will need to complete another questionnaire on the use and relevance of the cry and fuss clock and overall relevance of the COOL mobile app. At the end of the recording period, the primary caregiver will schedule an appointment with the PI. If the primary caregiver consents for the use of Fitbit, they will be provided Fitbit to record their vital parameters like heartrate and sleep pattern through the 14 days after enrolment. At the end of study visit,

the primary caregiver will discuss the data provided by the LENA recorder and the COOL mobile app with the PI and PI will use the data to explain to the primary care giver if there is any specific cry pattern that could be assessed based on the objective data from LENA. The Primary caregiver and PI will complete a questionnaire each on the use of the data provided by the LENA recorder during their discussion.

For up to 5 subjects in the study, if the primary caregiver consents for the use of Cocoon Cam they will be provided with the Cocoon Cam kit at screening visit. The primary caregiver will need to complete a training period in order to verify subject's primary caregiver's ability to properly connect, operate and upload data using the LENA recorders and uploader as well as the Cocoon Cam. As part of the training period, the primary caregiver will do 1-2 hours of recording using the LENA recorder and successfully upload the data into the LENA cloud server through the internet and use the Cocoon Cam for 1 day and able to start using the Cocoon Cam application. Once the study coordinator verifies that the LENA upload is successful and Cocoon Cam set-up is complete, the training and feasibility assessment will be considered as complete and the subject will be considered as enrolled. The primary caregiver of the enrolled subject will be provided access to the COOL mobile app and the recording period will start. During the recording period, in addition to the daily questionnaire, the primary caregiver need to enter cry and sleep time using the COOL app. At the end of 7th day and 14th day, the primary caregiver need to complete questionnaire on the usability of the Cocoon Cam.

3.3 Schematic diagram of study design (*Use of Fitbit and Cocoon Cam is based on Consent given)

Diagram 1: Subjects who are enrolled only with the LENA recorder

[figure not shown]
[figure not shown]

Diagram 2: Subjects who are enrolled with the LENA recorder and Cocoon Cam

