6.3.8 Questionnaires

Infant's crying pattern and caregiver experience of subject's crying and/or fussing for last 7 days before enrolment will be collected through primary caregiver reported questionnaires on the mobile app at enrolment.

The primary caregiver's feedback on the use and relevance of the data provided by the LENA recorder and their feedback on the level of engagement due to the content on the COOL mobile app will be collected through self-reported questionnaires at day 7 and 14.

A daily questionnaire on the average total minutes the subject cried/fussed and the time of the day the subject cried or fussed most based on primary caregiver's perception will be collected for 14 days from enrolment through primary caregiver reported questionnaires on the mobile app.

For the primary caregiver who consented for the use of Cocoon Cam, cry and sleep time for the infants around the clock will be collected using the COOL mobile app. The usability of the Cocoon Cam by the primary caregiver will be collected through questionnaire at day 7 and 14.

At the end of the study post clinic visit, a questionnaire to understand if the information from the LENA recorder helped to objectively articulate the primary caregiver's discussion with the PI will be collected through primary caregiver reported questionnaires on the mobile app.

At the end of the study post clinic visit, a questionnaire on feedback from the HCP on the usability and relevance of the cry and fuss data generated by the LENA recorder in their daily practice will be collected. For the primary caregiver who consented for the use of Cocoon Cam, a feedback from the HCP on the usability of the Cocoon Cam will also be collected.

6.3.9 *Data from Fitbit*

Vital parameters like heartrate and sleep pattern from Fitbit of the primary caregiver.

6.3.10 *Data from Cocoon Cam*

Sleep, Crying data captured by Cocoon cam and the usage data for the Cocoon Cam app .

6.3.11 *Study compliance*

Compliance is categorized as:

- Adherence in answering to the daily questionnaire
- Use of the LENA recorder
- Adherence to the visit window

6.3.12 *End of study evaluation*

Participants may be asked for their feedback on study participation. This is voluntarily and the encoded data will not be linked to the participants. Danone Nutricia Research will use the data to improve future studies. The encoded data will not be reported as study outcome parameter.

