7 PRODUCTS

7.1 Name and description of the product

LENA is a commercially available device that parents, pediatricians, speech language pathologists, and researchers use to obtain information about a child's language environment and language development. Its language statistics were validated in a large-scale study that established norms for words, turns, and vocalisations. The device is now modified to also record crying and fussing.

The LENA recorder model# 0121 used for this study is a lightweight, pocket-size, rechargeable electronic device. This recorder can be placed securely into the specially designed infant's clothing as provided by the Sponsor. The specially designed garments are washable and reusable. After 24-hour use and removal from the clothing, the recorder can be connected to the uploader, the data is uploaded to a cloud online platform and subsequently erased from the in-home recorder. The connection with the uploader also allows the recorder to be subsequently recharged. The infant's primary caregiver will be supplied with 2 identical recorders that will be used interchangeably (one recorder is recording while the other is recharging).

The COOL mobile app is a mobile application available to the primary caregiver during their period of enrollment in this study to answer questionnaires, view the cry and fuss clock generated from the LENA recorder data and to provide them insights on infant's crying and fussing.

For the cohort consenting for Fitbit and Cocoon cam, the primary caregiver will receive Fitbit and Cocoon camera as part of study product.

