2.6 Study outcome parameters

2.6.1 Primary outcome parameters

The rating by the primary caregivers on the use and relevance of the cry and fuss clock generated from the LENA system data and the rating by the primary caregiver on the level of engagement due to the content on the COOL mobile app.

The primary objective is measured by below variables all measured on a discrete 6-point scale ranging from 0 = not at all to 5 = Yes, very much represent the primary outcome:

- Use and relevance of the LENA recorder and COOL mobile app rated by the primary caregiver at day 14 will be reported (summary statistics)
- Engagement of the LENA recorder and COOL mobile app rated by the primary caregiver at day 14 will be reported (summary statistics)

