2.7 Database and data validation

The CRF (Cool web portal), diary and questionnaire data (Cool mobile application) (are collected based on the structure and platform listed in the Server Architecture Document version 1.0. Amazon Web Services (AWS) will be used for creation of hosting environment. Details of the database are as follows: Microsoft SQL Server 2017 (RTM) - 14.0.1000.169 (X64) Copyright (C) 2017 Microsoft Corporation Express Edition (64-bit). Data from LENA recorder is uploaded into the LENA cloud server using an uploader. The reports from the LENA processing are available in the LENA portal for download. The data from the LENA portal are downloaded and transcribed into graphical format using validated programs and uploaded into the Cool mobile application.

CRF, diary and questionnaire data are validated using automated edit checks and data validation steps as described in the Data Validation Plan.

Fitbit data (Sleep and Heart rate) will be exported from Fitabase for analysis at the end of the study.

Cocoon Cam data will be transferred from the Cocoon Cam cloud server and is detailed in Data Transfer Agreement for Cocoon Cam.

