3 PROTOCOL DEVIATIONS

All protocol deviations will be discussed prior to Database Lock. Possible deviations for this study are:

Description of Deviation	Deviation Type
Visit window deviation	Minor
Not all questionnaires completed	Minor
Enrolled with Cocoon Cam but failed to use Cocoon Cam during the study period	Minor

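### The plan describes no route other than the COOL app for the caregiver's Day 14 primary ratings and no sensitivity analysis for missing ones, so the primary mean may lean upward

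*Protocol*

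**What the plan says.** **What is rated.** SAP 2.6.1 makes the Day 14 caregiver ratings, on a 0 to 5 scale, the primary outcome. One covers use and relevance. The other is described as "Engagement of the LENA recorder and COOL mobile app rated by the primary caregiver at day 14 will be reported (summary statistics". Protocol 3.2 has the caregiver "complete another questionnaire on the use and relevance of the cry and fuss clock and overall relevance of the COOL mobile app" once 14 days have passed.

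**How the rating is returned.** Protocol 5.5.2 and 6.3.8 name the mobile app for the enrolment, daily and post-clinic caregiver questionnaires. For the Day 7 and Day 14 feedback, 6.3.8 says only that it "will be collected through self-reported questionnaires at day 7 and 14". Two other places point to the app. Protocol 7.1 describes it as "available to the primary caregiver during their period of enrollment in this study to answer questionnaires". SAP 2.7 assigns the CRF to the web portal and then lists "diary and questionnaire data (Cool mobile application". No paper, telephone or clinic alternative is described.

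**What happens to a missing rating.**
- SAP 4.1: one post-baseline measurement, for example one from LENA, is enough for the full-analysis set.
- SAP 5.2.2: the primary analysis uses that set and reports the number of missing observations.
- SAP 5.3 and 5.8: no imputation, and non-responders leave the denominator of the mean.
- SAP 3: "Not all questionnaires completed" is a minor deviation.
- No sensitivity analysis for missing ratings appears anywhere.

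**The concern.** As far as the documents show, the product being rated also carries the rating. Caregivers who have lost interest in the app, or cannot get it to work, are less likely to open it and answer. They are also plausibly the caregivers who would score engagement and usability low. Whether a rating exists can then depend on what it would have said. An observed-data mean does not correct for this, and the likely direction favours the product.

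The entry checks do not fully remove the risk. The second exclusion criterion screens out caregivers who cannot access the app at entry, not later disuse or failure. The training check in Protocol 3.2 verifies the LENA upload (and the Cocoon Cam set-up where used); access to the COOL app follows enrolment. A Day 14 rating that is never given cannot be reconstructed by analysis, and with about 20 families each one carries weight.

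**Working it through.** **1. The plan's own figure.** Inputs from Protocol 10.1 and SAP 2.5: SD 1.25, n = 20, half-width at most 0.70, two-sided 95% interval, probability 0.90.

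P(half-width ≤ 0.70) = P(χ² with n−1 df ≤ (n−1) × [0.70 × √n / (t₀.₉₇₅,ₙ₋₁ × 1.25)]²)

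- n = 20: 0.900 (0.896 if conditioned on the interval covering the mean). The stated 0.90 reproduces.
- 0.90 × 0.95 = 0.855, as stated.
- 20 / (1 − 0.20) = 25 enrolled, as stated.

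The same formula gives 0.80 with 18 ratings and 0.65 with 16. This is what fewer ratings would cost in precision, not an error in the plan.

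**2. Bias of the observed mean.** Let N caregivers be in the analysis set and k give no rating. Let those k have a mean d points below the raters' mean R. The full mean is [(N − k)R + k(R − d)]/N = R − (k/N)d, so the observed mean is too high by (k/N) × d.

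| N | k | d = 0 | d = 1 | d = 2 | d = 3 |
|---|---|---|---|---|---|
| 20 | 2 | 0 | 0.10 | 0.20 | 0.30 |
| 20 | 4 | 0 | 0.20 | 0.40 | 0.60 |
| 25 | 5 | 0 | 0.20 | 0.40 | 0.60 |

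For scale, 0.40 / 0.70 = 57% of the planned half-width, and d = 2 is 2 / 1.25 = 1.6 SDs, a large gap.

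**3. Effect on the interval.** Coverage of the full-set mean by the nominal 95% interval, from the noncentral t distribution with normal ratings and SD 1.25:

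- k = 2 of 20: 0.94, 0.90 and 0.84 for d = 1, 2 and 3.
- k = 4 of 20: 0.91, 0.78 and 0.57.

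**4. Bounds that need no d.** Take an illustrative observed mean of 4.0 on the 0 to 5 scale.

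- k = 2 of 20: from (18 × 4 + 2 × 0)/20 = 3.6 to (18 × 4 + 2 × 5)/20 = 4.1.
- k = 4 of 20: from (16 × 4 + 4 × 0)/20 = 3.2 to (16 × 4 + 4 × 5)/20 = 4.2.

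**5. Status of k and d.** Both are assumptions. SAP 5.8 has worked examples with 4 missing of 20 (an HCP item) and 2 missing of 20 (a 0 to 5 item). They illustrate how percentages and means are calculated and are not forecasts of non-response.

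**The case against.** A reader might infer that the Day 14 rating is collected solely inside the app, that a disengaged caregiver therefore returns nothing, and that the mean is biased towards engaged users. The documents do not support that much.

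- **Channel.** No sentence excludes another route, and the sections describing the Day 14 questionnaire name none. Details may sit in the caregiver questionnaire or the Data Management Plan, which are not among the documents. The web application in Protocol 12.3 is not shown to be a caregiver route, because SAP 2.7 gives the web portal to the CRF.
- **Contact.** A clinic visit is planned at Day 14 with a window of 7 further days (Protocol 6.2), and Appendix IV places the Day 14 questionnaire in that column. The site could recover a rating there; the plan neither provides for this nor rules it out.
- **App failure.** The post-clinic caregiver questionnaire is itself on the app, so a family that answers it has used the app late in the study. The enrolment and daily questionnaires are on it too, and daily adherence is a compliance parameter, so disuse would be noticed.
- **Visibility.** The number missing and the full rating distribution will be reported, and SAP Appendix 1 tabulates the primary outcome at Day 7 as well as Day 14. The study is descriptive and tests no hypothesis.
- **Size.** Neither k nor d has a source in the documents.

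All of this limits the point without removing it. Seeing disuse does not recover a rating. A count of missing ratings neither corrects nor bounds the mean. Nothing instructs the site to collect an outstanding rating at the visit.

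**Conclusion.** The point holds as a gap in the plan with a possible upward bias. It is not a demonstrated bias. The app is the only caregiver channel described, a family can be in the primary analysis set without a rating, and no fallback or sensitivity analysis is planned. The excess in the mean is (k/N) × d: with N = 20, 0.10 for k = 2, d = 1 and 0.40 for k = 4, d = 2, and nothing if non-raters would have scored like raters. The direction rests on the assumption that low engagement makes both a missing rating and a low rating more likely. That is plausible but not established by the documents.

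A reader might also infer that the sample size is wrong because "This study plans to have 20 completed subjects" counts completers and not ratings. It is not: the precision stated for 20 reproduces. The study is not invalidated, but this weakness in its headline result is cheap to prevent.

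**What to change.** **Protocol 3.2, 6.1 and 6.3.8.** State the channel for the Day 14 rating. If no in-app rating has arrived, have the caregiver self-complete the same primary items by email, or on paper at the existing end-of-study visit before the discussion with the PI. Use the telephone only if neither is possible. Record the mode, the date and the reason. Protocol 3.4 already provides for telephone and email contact. This applies to families still in the study, since Protocol 4.6.2 stops new data collection, other than safety follow-up, after discontinuation.

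**SAP 5.2.2.** Analyse all Day 14 ratings whatever the mode, report n by mode, and show an in-app-only row as a sensitivity analysis. Add a simple bounding row for ratings still missing, for example missing set to 0, and the Day 7 rating carried forward.

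**What not to do.** Do not redefine the 20 completers as raters only. That would fill the target with the selected group that raises the concern.

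**Cost.** Some wording in both documents and a few emails or paper forms handled by existing site staff. The downside is that a few ratings come by a second mode and up to 7 days later. The recorded mode and date flag these, and the in-app-only row shows their effect.
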